## PRÉCIS

**Background:** AIDS-related primary central nervous system lymphoma (AR-PCNSL) is an Epstein-Barr virus (EBV)-driven lymphoproliferative process that typically results in death within a few months. Essentially all of the cases are immunoblastic CD20+ tumors, and occur once the CD4+ cells have fallen to below 50 cells/mm^3. Highly active antiretroviral therapy (HAART) can result in immune reconstitution that decreases the risk of AR-PCNSL. However, a subset of HIV-infected patients still develops AR-PCNSL, often because they are unaware that they are HIV infected, or they do not take HAART. Treatment options for such patients are limited. In the non-AIDS setting, chemotherapy has become the standard of care for primary central nervous system lymphoma (PCNSL) and late neurocognitive decline consequent to radiotherapy can be avoided by such approaches. In the pre-HAART era, AR-PCNSL was generally treated with whole brain radiotherapy, however death due to recurrent lymphoma or to other AIDS complications occurred prior to the potential manifestations of late occurring radiation-related neurotoxicity. Radiation-sparing approaches have not been studied in AR-PCNSL in the HAART era, where advances in antiretroviral therapy have made curative intent chemotherapy feasible for most patients with HIV infection.

**Objectives:** The primary objective of this study is to estimate the fraction of patients with AR-PCNSL receiving experimental treatment consisting of HAART, combined with rituximab, high-dose methotrexate and leucovorin who are alive and without recurrent lymphoma or severe cognitive problems at two years.

**Eligibility:** HIV-infected, age 18 years or older, AR-PCNSL that has not previously been treated, and be able to give informed consent or have a durable power of attorney who can provide informed consent, HIV profile that makes them likely to respond to HAART. There are a number of other specific inclusion and exclusion criteria, in part to exclude patients who would be unlikely to tolerate the therapy.

**Design:** Phase II pilot study investigating high-dose methotrexate-rituximab given with leucovorin rescue and HAART as a treatment for AR-PCNSL. Evaluation will include quantitative measurement of lymphocyte subsets, quantitative polymerase chain reaction (PCR) of HIV and EBV viral loads (including both blood and cerebrospinal fluid in the case of EBV) to assess immune response and anti-viral effects. Tumor evaluation with brain magnetic resonance imaging (MRI) and brain fluoro-2-deoxy-d-glucose positron emission tomography (FDG-PET scans) will be used for staging and response assessment. Longitudinal neuropsychologic testing after complete responses are documented will serve to evaluate neurocognitive parameters post therapy. Chronic administration of HAART and longer-term evaluation of immune system parameters will be studied as part of an overall assessment of the therapy. Patients with AR-PCNSL who cannot receive high-dose methotrexate due to poor renal or cardiac function will receive HAART and “Radiation-Sparing Best Available Care”, generally consisting of dose-dense rituximab, and will be evaluated as a separate cohort for additional secondary endpoints.

## 1 INTRODUCTION

### 1.1 STUDY OBJECTIVES

#### 1.1.1 Primary

1.1.1.1 The primary objective of this study is to preliminarily estimate the fraction of patients with primary brain lymphoma receiving experimental treatment consisting of HAART with R-HD-MTX who are alive and without recurrent lymphoma or severe cognitive problems (as defined by Neurological Function Class 3 in Appendix 2) at two years. It will also be important to determine if this fraction may be sufficiently high for further investigation.

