**Figure 1: Study Schema: Eligibility Evaluation and Initial Therapy**

### **3.2 PHASE II STUDY DESIGN FOR HIGH-DOSE METHOTREXATE WITH LEUCOVORIN RESCUE AND RITUXIMAB**

Induction treatment cycles with rituximab, high-dose methotrexate and leucovorin will be administered every 2 weeks for 6 cycles. Two additional consolidation cycles of high-dose methotrexate without rituximab will be administered at 4 weeks and 8 weeks following completion of the combined therapy.

MRI will be repeated at the end of cycles 2, 4, 6, and 8, and additionally as clinically indicated. At the time of first evidence for complete tumor response by MRI criteria, FDG-PET scan and EBV DNA assessments of the blood and CSF will be repeated. If there is not a complete response by end of cycle 6, patients will be categorized as treatment failures and will not receive the two additional high-dose methotrexate doses. At end of treatment, restaging by MRI will be performed once every 2 months x 3; then once every 3 months x 6; then once every 6 months x 2; then as clinically indicated or annually up to year 5. After this period, clinical evaluations may continue and restaging

performed if clinical suspicion of CNS pathology. Additionally, FDG-PET scan will be repeated as outlined in section 3.8.4.2. (See also Appendix 3).

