## 5.3 RESPONSE CRITERIA

Response criteria are based on published standards for phase II studies of supratentorial malignant glioma and a modification of the response assessment of aggressive non-Hodgkin's lymphoma by integrated international workshop criteria and fluorine-18 – fluorodeoxyglucose positron emission tomography, and an international workshop to standardize baseline evaluation and response criteria for primary CNS lymphoma. Cross-sectional measurements of tumors will be used to assess baseline and responses.

- 5.3.1 Complete Response - disappearance of all enhancing lesions on MRI of the brain, negative FDG-PET scan persisting for at least 4 weeks in patients who were off corticosteroids, negative CSF cytology and neurologically improved from baseline.
- 5.3.2 Complete Response Unconfirmed (CRu) – either a CRu, PR or SD by MRI criteria with a completely negative FDG-PET off steroids, and negative CSF cytology. If there is no evidence of progression while off steroids for 4 months, response will be reclassified as CR.
- 5.3.3 Partial Response
  - 5.3.3.1 A reduction of enhancing tumor volume by more than 50% maintained for at least 4 weeks, steroids stable or reduced, and neurologically stable or improved with positive FDG-PET, or

- 5.3.3.2 Normalization of MRI, negative FDG-PET, but with persistent disease by CSF cytology.
- 5.3.4 Progressive disease - an increase of tumor volume of more than 25% or occurrence of new lesions, or neurologically worse, steroids stable or increased.
- 5.3.5 Stable disease – not meeting the criteria for complete response, partial response, or progressive disease and with a positive FDG-PET
- 5.3.6 Treatment failure - progressive or stable disease, relapse after initial response, death, or discontinuation of chemotherapy because of complications or because of patient's or Investigator's decision. Patients who require radiotherapy will be considered treatment failures for purposes of the protocol, regardless of long-term outcome.
- 5.3.7 Substantial brain dysfunction and cognitive problems (as referred to in sections 1.2.3 and 7.4.4) that will define treatment failure refer to post-treatment recurrent brain lymphoma, treatment related functional brain pathology, and/or neurologic function class 3 or 4 as defined in Appendix 2: Neurological Function Class.

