#### 6.1.3 Sample Size and Accrual Limits

The primary objective of this study is to preliminarily estimate the magnitude of, and determine if there is potentially an acceptable fraction of, patients with primary brain lymphoma, who will receive the experimental treatment consisting of HAART with high-dose methotrexate-rituximab who are able to survive without recurrent lymphoma or severe cognitive problems (as defined by Neurological Function Class 3 in [Appendix 2](#)) for at least two years.

The goal of this limited size pilot trial is to enroll 15 evaluable patients who receive all treatment, including high-dose methotrexate. With conventional treatments, including whole brain irradiation, it would be expected that only 25-30% of all such patients with this disease would be alive without recurrent brain lymphoma and free of cognitive problems at the end of two years (a satisfactory result, but in too small a fraction of patients). We believe it quite possible that by using this particular chemotherapy, as many as 65% would be alive without recurrent lymphoma and without cognitive problems after two years. Sixty five percent is a figure chosen that is within range of the outcome expected in high-risk patients with non-AIDS primary brain lymphoma treated with high-dose methotrexate based strategies. With 15 patients, using a one-sided 0.1 alpha level exact test of binomial proportions, there is 88% power to rule out 30% with a satisfactory result after two years in favor of 65% with a satisfactory result. Should the results appear at all promising, even if not to this degree, the strategy may be taken to the AIDS Malignancy Consortium to see if they are interested in pursuing the idea in a larger, more definitive fashion. The results of this study will be weighed against the best available data from other studies to make a reasonable determination as to how to proceed with or modify this approach for further development.

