Additionally, up to 10 additional patients who are not eligible to receive high-dose methotrexate may be accrued in the “Radiation-sparing Best Available Care” Cohort. The patients enrolled in this limited size cohort will be evaluated for the same endpoints as in the main cohort receiving high-dose methotrexate, but given the limited number of patients who will enroll into this cohort, all analyses in this cohort will be considered hypothesis generating and exploratory. Accrual to this cohort will close when 15 evaluable patients have been enrolled in the main cohort.

All secondary endpoints will be evaluated using explorative techniques, and will be reported as exploratory, since the study is not designed to address any of these points with more than minimal power.

Since part of the treatment strategy is aimed at HIV suppression and immune reconstitution, up to 3 patients who are non-adherent with HAART within the first 9 months of therapy may be replaced. It can often take up to 9 months to adjust medications for purposes of optimizing medication tolerance and adherence to antiretroviral therapy. Patients who are clearly non-adherent and thus are unable to maintain an HIV viral load of <5000 copies HIV mRNA/mL plasma and do not have an increment in the CD4+ cells to above 75/mm^3 by the end of 9 months may be replaced. Patients who maintain lower HIV viral loads but do not have adequate immune recovery will not be replaced, and will be considered treatment failures in the event of tumor recurrence. Informal comparison will be made between those who are HAART naive at entry and those who are antiretroviral experienced.

This is a rare condition, and it is expected to take between 6 and 10 years to enroll 15 patients onto this trial in the main cohort and up to 10 in the cohort not receiving high-dose methotrexate. Up to three patients may be replaced if during the first 9 months they are clearly non-adherent with HAART as described above. Thus an accrual ceiling of 28 patients will be used.

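### The rules that decide the primary two-year outcome conflict on stopping chemotherapy after complete response, on who is in the denominator, and on Neurological Function Class 4

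*Combined protocol and SAP*

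**What the plan says.** **Endpoint.** Section 1.1.1.1 sets out to estimate the fraction of patients "who are alive and without recurrent lymphoma or severe cognitive problems (as defined by Neurological Function Class 3 in Appendix 2) at two years". Section 6.1.3 repeats this, with the same reference to Class 3, as surviving without these events for at least two years.

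**Planning rates.** Both rates in 6.1.3 describe a two-year state. Under conventional treatment, 25-30% "would be alive without recurrent brain lymphoma and free of cognitive problems at the end of two years". Under the study regimen, "as many as 65% would be alive without recurrent lymphoma and without cognitive problems after two years".

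**Failure rules elsewhere.**
- 5.3.6: "Treatment failure - progressive or stable disease, relapse after initial response, death, or discontinuation of chemotherapy because of complications". The sentence goes on to include a decision by the patient or investigator. Radiotherapy is a failure whatever the long-term outcome.
- 5.3.7: failure includes Neurological Function Class 3 or 4. It cross-refers to 1.2.3 and 7.4.4, not to 1.1.1.1 or 6.1.3.
- 3.2: "If there is not a complete response by end of cycle 6, patients will be categorized as treatment failures".
- 3.4.2.9: methotrexate toxicity that prevents further methotrexate before complete response (CR) is a failure.
- 3.7 and 3.10.1: radiotherapy is a failure for statistical purposes, and any other additional therapy for the lymphoma is a failure for the study.

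**Denominator.** Section 6.1.3 plans to "enroll 15 evaluable patients who receive all treatment, including high-dose methotrexate". It allows that "up to 3 patients who are non-adherent with HAART within the first 9 months of therapy may be replaced". Patients with lower viral loads but poor immune recovery "will not be replaced, and will be considered treatment failures in the event of tumor recurrence", which is the section's only use of the term treatment failures.

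**The concern.** Estimating this fraction is the primary objective. For a few foreseeable patients the stated rules give different answers, and 6.1.3 cites neither 5.3.6 nor 5.3.7 to settle them.

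1. **Stopping after CR.** Section 3.5 lists several reasons for stopping, among them impaired methotrexate clearance, low creatinine clearance and long dose delays. MRI after cycles 2 and 4 means that CR can come before the end of treatment. A patient who then stops and is well at two years is a success by the endpoint and a failure by 5.3.6. Section 3.4.2.9 does not help, because it covers stopping before CR.
2. **Denominator.** If receiving all treatment is a condition for being counted, early stoppers leave the denominator, and the fraction is then taken over patients selected for tolerating the regimen.
3. **Class 4.** Appendix 2 makes Class 4 worse than Class 3. Read literally, the endpoint excludes only Class 3.

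At stake is an estimate from 15 patients whose value depends on which rule the analyst follows, set against a benchmark that is a two-year state.

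**Working it through.** **Step 1. Reproduce the plan's figure.** Inputs from 6.1.3: n = 15, one-sided alpha 0.1, exact binomial test, p0 = 0.30, p1 = 0.65. The cut-off is the smallest r with P(X ≥ r | 15, 0.30) ≤ 0.10.
- P(X ≥ 7 | 0.30) = 0.131, too large.
- P(X ≥ 8 | 0.30) = 0.050, so r = 8.
- Power = P(X ≥ 8 | 0.65) = 0.887.

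The stated 88% is right.

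**Step 2. Set the rules side by side.**

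| Patient | 1.1.1.1 and 6.1.3 endpoint | Failure rules | 6.1.3 denominator |
|---|---|---|---|
| Stops chemotherapy for complications after CR, well at two years | Success | Failure (5.3.6); not covered by 3.4.2.9 | Possibly outside the 15 |
| Alive, lymphoma-free, Class 4 at two years | Not excluded if read literally | Failure (5.3.7) | Counted |
| Receives radiotherapy, well at two years | Success if read alone | Failure (3.7, 5.3.6, 3.10.1) | Settled as failure |
| Receives other additional lymphoma therapy, well at two years | Success if read alone | Failure (3.10.1) | Settled as failure |

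The first two rows are open. The last two are not.

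**Step 3. Effect of one reclassified patient.** 1/15 = 6.7 points.
- 8/15 = 53.3%, exact 95% CI 26.6% to 78.7%, p = 0.050.
- 7/15 = 46.7%, exact 95% CI 21.3% to 73.4%, p = 0.131.

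The test result changes only if the count is exactly 8 before reclassification. At a true 65%, P(X = 8) = 0.8868 - 0.7548 = 0.132.

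**Step 4. Power if would-be successes are relabelled.** The documents give no frequency, so the share d is assumed. The counted rate is 0.65 × (1 - d), and power is P(X ≥ 8) at that rate.
- d = 5%: rate 61.75%, power 82.6%.
- d = 10%: rate 58.5%, power 75.0%.
- d = 20%: rate 52.0%, power 56.3%.
- If 65% is already net of such failures: no loss.

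Relabelling does not inflate false positives. At p0 the chance of passing falls from 5.0% to P(X ≥ 8) at 0.30 × (1 - d), which is 3.7%, 2.7% and 1.4% for the same values of d.

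**Step 5. Effect of dropping early stoppers.** Under 5.3.6 every stopper is a failure, so removing stoppers can only raise the fraction. Illustration, all assumed: the true success rate among all who start is 30%, a share q stop, none of the stoppers succeed, and 15 non-stoppers are counted. The rate among those counted is 0.30/(1 - q).
- q = 10%: rate 33.3%, chance of passing 8.8%.
- q = 20%: rate 37.5%, chance of passing 15.9%.
- With everyone counted: 5.0%.

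**The case against.** The strongest case is that the documents, read together, already settle most of this.

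- A reader might infer that every failure rule based on treatment course is left hanging. That is not so. Radiotherapy is tied to the statistics in 3.7, and 3.10.1 covers any other additional therapy.
- The partial-response mismatch between 3.2 and 5.3.6 looks like a fourth conflict, but it is very narrow. Under 5.3.2 a partial response on MRI with negative PET off steroids and negative cytology is an unconfirmed complete response (CRu). Under 5.3.3 a partial response implies a positive PET or persistent disease on cytology. Most such patients would go on to further therapy and be failures under 3.10.1. Remission on HAART alone, mentioned in 1.2.4.2, rests on case reports. This is a wording mismatch, as is the absence of CRu from 3.2 when 3.8.5.3.3 expects CRu patients to reach cycle 8.
- The phrase about surviving for at least two years in 6.1.3 reads as event-free over the period, which narrows the contrast between status and course. It does not mention discontinuation, so the first conflict stands.
- The ceiling of 28 is 15 + 10 + 3, and 6.1.3 gives HAART non-adherence as its only ground for replacement. The words about receiving all treatment may only separate this cohort from the one without methotrexate. It is therefore not shown that early stoppers would be dropped, only that the text permits that reading.
- Class 4 is probably a drafting slip, given 5.3.7. It still stands in the endpoint wording in both 1.1.1.1 and 6.1.3.
- A reader might infer that the trial is underpowered. The documents do not support that: 88% is correct, and the losses in step 4 need an assumed frequency and a 65% that is not already net.

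**Conclusion.** The concern holds for three items: discontinuation after CR, the reading of the denominator, and Class 3 against Class 3 or 4. The first is a direct contradiction between stated rules, the second an ambiguity that could bias the fraction upward, and the third a probable slip in the primary endpoint.

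The certain part of the size is 6.7 points per reclassified patient, with the test affected only at 8 against 7 of 15. The power figures of 82.6%, 75.0% and 56.3%, and the chances of passing of 8.8% and 15.9%, are illustrations under assumed frequencies.

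Severity is minor to moderate. Section 6.1.3 sets no binding gate and says that the approach may go forward on weaker results. The issue therefore bears on how the estimate is read more than on a decision.

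**What to change.** - In 1.1.1.1 and 6.1.3, replace Class 3 with Class 3 or 4, and cite 5.3.6 and 5.3.7 as the failure definition for the primary outcome. Discontinuation for complications or by decision then counts as failure.
- State in 6.1.3 that every main-cohort patient who starts high-dose methotrexate stays in the denominator, except the up to 3 HAART replacements. Reconcile this with the wording on receiving all treatment and with the censoring in 1.2.5.
- Reconcile 3.2 with 5.3.6 for partial response and with 3.8.5.3.3 for CRu, for classification only.
- Because the 25-30% benchmark is a two-year state, report the status-only count as a sensitivity analysis. List the reclassified patients and any whose two-year status is unknown.

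The cost is a few sentences and one extra tabulation. Sample size, cut-off and planning rates do not change. There are two downsides. The observed fraction may be slightly lower. Two-year status may also be missing for some of the patients whom the sensitivity analysis needs, because 3.10.1 returns patients needing further therapy to referring physicians when possible, 3.7 limits follow-up of second-line patients who do not take part in neuropsychometric testing, and 3.11.2 takes those who refuse oncologic therapy off study.

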#### 1.1.2 Secondary

1.1.2.1 To describe the acute toxicities associated with administering a regimen of high-dose methotrexate with leucovorin and rituximab with HAART in patients with AR-PCNSL

1.1.2.2 To estimate the complete response rate, progression-free, disease-free, and overall survivals to high-dose methotrexate with leucovorin and rituximab given with HAART in patients with AR-PCNSL

1.1.2.3 To describe HIV disease, EBV infection, and lymphoma tumor biology

1.1.2.4 To assess the neurotoxicity associated with this regimen by monitoring neuropsychologic function over time through longitudinal psychometric testing

1.1.2.5 To assess overall survival, progression-free survival, and long-term neurocognitive outcomes in patients with AR-PCNSL in who high-dose methotrexate is contraindicated and are therefore treated with radiation-sparing therapy consisting of dose-modified, dose-dense rituximab combined with HAART but no high-dose methotrexate.

1.1.2.6 To assess overall survival and long-term neurocognitive outcomes in patients with AR-PCNSL who receive “Radiation Sparing Best Available Care”, consisting of HAART and any additional first or second line radiation-sparing approaches

### 1.2 BACKGROUND AND RATIONALE

#### 1.2.1 Biology, Epidemiology and Scope of Problem

AIDS-related primary central nervous system lymphoma (AR-PCNSL) is a rare but lethal complication of advanced HIV disease. Essentially 100% of AR-PCNSL is Epstein-Barr virus (EBV)-associated B-cell tumors. They occur almost exclusively in persons with CD4+ cells that are depleted below 50 cells/mm^3. Histologically, these tumors are overwhelmingly represented by diffuse large B-cell lymphomas (DLBCL), typically the immunoblastic variant with pathobiological markers suggesting histogenic derivation from post germinal center B-cells at late stages of maturation. Thus, most cases show absence of bcl-6 protein while MUM1 and CD138/syndecan-1,

and bcl-2 are expressed. While essentially all cases are EBV-associated, the EBV expression pattern in AR-PCNSL can differ. Moreover, the histological and pathobiological characteristics of AR-PCNSL appear to segregate according to EBV expression patterns. In cases that are negative for LMP-1 expression, bcl-6 protein is expressed, whereas bcl-2 is not. This pattern is invariably associated with a large non-cleaved morphology similar to HIV-negative cases, and suggests germinal center B-cell histogenic derivation. In contrast to AR-PCNLS in which a proportion of tumors appear to derive from non-germinal center B-cells, in HIV-unrelated PCNSL in which EBV is almost never found, the pattern of biologic markers is essentially always most consistent with germinal center histogenic derivation. Treatment outcome and prognosis in AR-PCNSL may be heterogeneous and in part related to these biologic characteristics as has been shown in systemic HIV-unrelated NHL. In general, a more favorable prognosis in peripheral NHL is seen in tumors that derive from germinal center-like B-cells. While this appears also to be the case in PCNSL, there is uncertainty because of other factors involved in AIDS that affect prognosis. Determination of tumor biology in AR-PCNSL is important toward understanding treatment outcomes, and forms part of the rationale for tumor acquisition on this study.

Prior to the availability of highly active antiretroviral therapy (HAART), nearly 20% of all lymphomas in AIDS patients were AR-PCNSLs. The relative risk of developing PCNSL in AIDS was 1000-fold that of the non-AIDS population. As a consequence of better preserved immune function with HAART, the incidence of AR-PCNSL has fallen substantially. In the pre-HAART era the incidence was more than 300% higher than currently seen. Similarly, a much smaller proportion of AIDS-related lymphomas (ARL) are PCNSL, because the decrease in incidence of this tumor is greater than for the other ARLs. HAART has also favorably affected survival in patients with ARL, including AR-PCNSL. Before HAART availability, the median survival after diagnosis of AR-PCNSL was 2 to 3 months. However, six-fold or greater increases in survival are reported when HAART is given compared to cases not treated with HAART, though this is not a consistent finding. While AR-PCNSL currently affects relatively few individuals, this may not be a lasting phenomenon as the AIDS epidemic evolves. The number of HIV-infected individuals in the United States continues to increase. At present, estimates suggest at least 950,000 Americans are infected, a quarter of whom do not know their seropositive status. These people often do not receive antiretroviral therapy until after they are confronted with opportunistic disease, including AR-PCNSL. As a consequence, AR-PCNSL may continue to be a serious medical problem, especially in medically underserved demographic groups most affected by the HIV epidemic. In such resource poor settings where treatment access is often delayed and HAART is not readily available, AR-PCNSL continues to be a rapidly lethal complication of AIDS. In addition to the changing demographics of persons with AIDS, there has been more than a 50% increase in the prevalence of persons living with AIDS because of the increased longevity consequent to HAART. Since 1996, when HAART was introduced, the number of persons with AIDS in the United States increased from approximately 200,000 to nearly 400,000^22. There is thus an expanding at-risk

population for malignant complications of AIDS, now the major form of HIV-related morbidity and mortality in resource-rich societies where HAART is commonly used. Additionally, in Western Europe, the proportion of primary brain lymphomas as an AIDS-defining condition in HIV-infected patients has remained relatively steady in the period 1988-2000^30. Therefore, even though this tumor is currently rare, it is quite conceivable that the absolute numbers of cases of AR-PCNSL will increase consequent to a number of issues. With increased longevity there may be an overall increase in lifetime risk of malignant complications of HIV disease. As the AIDS epidemic continues to shift to medically underserved populations, individuals may be more likely to first present with complications related to advanced immune depletion, such as AR-PCNSL.

